Study Team: [name] (RPCI subcontract) and [name] will manage the science and *WC Services* activities, respectfully, as MPIs. The *WC Services* to Medicaid clients will be conducted by experienced team members contracted from the NWP (see Budget Justification). The pilot efficacy study benefits from the expertise of assembled colleagues Drs. [name] (Statistician), [name] (Consultant) and [name] (Consultant). The entire process and especially the feasibility assessments will be reviewed under the guidance of a five-member advisory board designed to offer expertise and counsel regarding 1) Technology transfer and potential commercialization issues (RPCI, [name]); 2) Needs and concerns of the health insurance industry (YourCare, [name]); 3) Needs and concerns of primary care clinical practices (MCCC, [name]/[name]); and 4) Science and clinical issues of colonoscopy and CRC screening (RPCI, [name]).

Aim 1: Test the feasibility of WC Services to achieve CRC screening for non-adherent

[figure not shown]
Medicaid clients. Based on previous experience and research (see Bios, Facilities), we hypothesize that we will be able to combine multi-level services to effectively assist $\geq 65\%$ of Medicaid clients from health insurer and clinical partners to obtain CRC screening in a 6-month trial during this Phase I. Achieving the milestones and benchmarks in Aim 1 will provide proof that we can improve screening metrics and meet the needs for our potential customers.

Partners, Recruitment and Participants. Witness CARES, LLC has established relationships with Mercy Comprehensive Care Center (MCCC), a local primary care practice serving a high proportion of Medicaid patients, and YourCare Health Plan, a Medicaid Managed health insurance company serving Buffalo, NY (see Facilities and Resources) to conduct this Phase I study (see Letters), and we will rely upon our Scientific Advisory Board (see Letters) to guide the conduct of the study, assuring that we are meeting the needs of customers, providing optimal services for clients/patients and truly achieving our feasibility measures in this study to effectively move forward into Phase II.

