6 TARGET ACCRUAL AND STUDY DURATION

From a list of approximately 2000 unscreened individuals from insurer and primary care patient lists (acquired through a Business Association Agreement), we will contact and enroll a maximum of 200 participants. Accrual is expected to take up to 2 years.

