8 STATISTICAL ANALYSIS METHODOLOGY

AIM 1: Assessment and Evaluation. After Navigators have contacted and assessed client CRC screening needs by phone for providing WC Services, they will invite and consent clients to complete the study survey to collect prospective predictor assessment measures for which participants will be incentivized with a \$20 retail gift card, a method we have found successful in previous studies. A process and system for contacting, monitoring and then assessing satisfaction of clients with services will be conducted based on current mammography services. Witness CARES, LLC will be establishing a new and more comprehensive appointment scheduling monitoring system for this feasibility study to enhance measures currently used by NWP in order to improve the ability to track and document all CRC screening services and outcomes for future development. We currently have metrics for navigation and screening that will be revised for colonoscopy and stool test navigation and colonoscopy appointment

scheduling. We will use current tracking measures for accruals and outcomes and assess these weekly and monthly. We will closely monitor number of client contacts and time requirements to determine potential cost effectiveness and feasibility measures. Colonoscopy and FIT completion will be monitored and then validated by YourCare and MCCC. Basic frequencies and descriptive statistics will be used for this analysis. We will compare outcomes from YourCare and MCCC clients. Upon completion of CRC screening, satisfaction surveys will be conducted by Call Center staff for at least 60% of clients in order to assess *WC Services* acceptability, merit and suggestions for revisions. If clients prefer, these satisfaction surveys can be sent via Survey Monkey and completed on Smartphones. The Call Center will also obtain brief satisfaction and assessment surveys from GI practices and Primary Care Physicians treating Medicaid clients referred through *WC Services*.

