Expected outcomes of Aim 1 will prove whether or not *WC Services* can achieve $\geq 65\%$ CRC screening of clients reached. **Milestone 1a:** Achieve colonoscopy by a minimum of 60 out of 200 ($\geq 30\%$) patients contacted. **Milestone 1b:** Achieve CRC stool screening for 70 of the 140 colonoscopy non-adherent clients (50% of clients refusing/ineligible for colonoscopy). Beyond these milestones, additional **feasibility benchmarks** include: a) Acceptance/satisfaction by clients per client satisfaction phone surveys; b) Acceptance/satisfaction by YourCare and MCCC per self-report and any screening metrics improvement; c) Navigation services, number of screening tests per week/month, hours spent for cost analysis; d) Acceptance/satisfaction by GI physicians and facilities per self-report, number and quality of bowel preps and no-shows; e) Process evaluation of all. **Milestone 1c:** *WC Services* will be revised based on outcomes and benchmark measures from Aim 1, to produce a new prototype to test in a larger randomized study in Phase II.

AIM 2: Proposed Data Analysis (Milestone 2b). Update the Screening Engagement Model: Utilizing standard Bayesian methods, the data collected in Aim 1 from the (expected) $n=160$ intent-to-screen clients will be used to: A) update the coefficients of the Screening Engagement Model; and B) determine whether PAM, POC and NSAP measures should be incorporated. The performance of the updated model will be assessed using the AUC, sensitivity, and specificity (with 95% confidence intervals as appropriate). If the AUC of the resulting model is 0.8 (or 0.9), indicating reasonable performance, then the corresponding 95% confidence interval width would be 0.14 (or 0.10). *FIT versus COL:* Within the sub-set of subjects that were screened, measures will be compared between those who chose FIT versus COL using the Mann-Whitney U test. In Aim 1 we expect 60 COL and 70 FIT subjects, which provides 80% power (at $\alpha=0.05$) to detect a 0.5 standard deviation difference. Additionally, a multi-variable logistic regression model may be considered to identify potential independent factors associated with screening choice.

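### Aim 1 is said to prove whether at least 65% of clients are screened, but the planned analysis is descriptive and gives no measure of uncertainty for that rate

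*Combined protocol and SAP*

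**What the plan says.** Section 8 (Statistical Analysis Methodology), under the expected outcomes of Aim 1, begins "Expected outcomes of Aim 1 will prove whether or not" and goes on to a target of at least 65% screening among clients reached. Two numerical milestones follow. Milestone 1a is "Achieve colonoscopy by a minimum of 60 out of 200". Milestone 1b is "Achieve CRC stool screening for 70 of the 140 colonoscopy non-adherent clients".

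The method is given earlier in the same section: "Basic frequencies and descriptive statistics will be used for this analysis". The section adds a comparison of outcomes between the insurer's and the clinic's clients, without naming a method. It gives no confidence interval, test, null rate, significance level or power for the 65% rate.

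Inferential quantities appear only for Aim 2. The 80% power figure beside the sample size in section 5 refers the reader to the Aim 2 analysis, and the 95% intervals in section 8 are for the performance of the prediction model.

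On sample size, section 6 says "we will contact and enroll a maximum of 200 participants", whereas section 9 has calls continue until at least 200 clients are reached.

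**The concern.** The plan promises a yes-or-no conclusion about a rate, but its analysis produces only an observed proportion. Two hundred clients leave several percentage points of sampling error on either side of that proportion, and nothing in the Aim 1 analysis would tell a reader so.

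The result goes into the Phase I report and is meant to position the sponsor for a randomized Phase II evaluation. An observed 65% could be reported there as proof while being compatible with a rate of about 58%. In the other direction, an observed rate just under 65% could be reported as proof of failure while being compatible with a rate of 70%.

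**Working it through.** **Inputs.** From section 8: 65% target, 60 of 200 colonoscopies, 70 stool tests among 140 clients without colonoscopy. Assumed: n = 200, and clients independent with a common rate.

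**1. The plan's own figure.** (60 + 70)/200 = 130/200 = 65.0%; equivalently 0.30 + 0.70 × 0.50 = 0.65. The target is the sum of the two milestones, with no margin added.

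**2. Precision of a result on target.** The Clopper-Pearson limits for x of n are the 2.5% quantile of Beta(x, n − x + 1) and the 97.5% quantile of Beta(x + 1, n − x).

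| Result | Observed | Exact 95% CI |
|---|---|---|
| Overall, 130/200 | 65.0% | 58.0% to 71.6% |
| One short, 129/200 | 64.5% | 57.4% to 71.1% |
| Colonoscopy, 60/200 | 30.0% | 23.7% to 36.9% |
| Stool test, 70/140 | 50.0% | 41.4% to 58.6% |

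The overall rate is known to about ±7 points. The intervals for 130 and 129 are almost the same, so one client cannot separate proof from disproof. The stool-test row treats 140 as fixed; in the study it will be whatever number remains without colonoscopy.

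**3. Behaviour of a pooled rule.** The documents state no pass rule. Suppose it is 130 or more of 200, so that P(pass) = P(X ≥ 130) with X ~ Binomial(200, p).

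| True rate p | P(pass) |
|---|---|
| 58% | 2.6% |
| 60% | 8.4% |
| 62% | 21.2% |
| 63% | 30.6% |
| 64% | 41.5% |
| 65% | 53.2% |
| 70% | 94.6% |

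At a true 65% the target is missed 100% − 53.2% = 46.8% of the time.

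**4. Behaviour if both milestones must be met.** Let X ~ Binomial(200, a) be colonoscopies and, given X, let Y ~ Binomial(200 − X, b) be stool tests among the rest. The overall true rate is a + (1 − a)b. A pass needs X ≥ 60 and either Y ≥ 70 (1b read as a count) or Y ≥ half of 200 − X (1b read as 50%).

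| a | b | Overall | Pass, count | Pass, 50% |
|---|---|---|---|---|
| 28% | 47.2% | 62% | 5.8% | 7.9% |
| 29% | 49% | 63.8% | 12.7% | 17.2% |
| 30% | 50% | 65% | 19.8% | 27.3% |

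The first row gives the 6-8% quoted for a true 62%. Other splits with the same overall rate move it slightly: 30%/45.7% gives 5.3% and 9.0%, and 27%/48% gives 5.0% and 6.4%.

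Under the pooled rule a pass is fairly likely when the true rate is a little below 65%. Under the joint rule the plan would usually fail at exactly the rates it was designed around.

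**The case against.** The strongest defence is that this is a feasibility pilot ahead of a randomized Phase II. Frequencies set against milestones are an acceptable pilot analysis, and whether 65% of the clients actually reached were screened is settled by counting. No stated decision turns on crossing 65%: under milestone 1c the services are revised from the findings whatever the rate, and a reader of the report could work out an interval from the counts. Much of this stands. The descriptive analysis is not itself the defect. What remains is a claim of proof about what the services can achieve, which is a statement beyond the clients counted, with no precision attached.

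Three stronger readings are tempting, and the documents do not support them.

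- **That a true rate below 65% would often be declared proven.** This needs the pooled rule, which is inferred, and a true rate within about 3 points of the target. The chance is 8% at 60% and under 3% at 58%. If both milestones are required, the more likely error is failing at a true 65%.
- **That section 5 makes the same claim about the 65% rate.** Its sentence is "Achieving the milestones and benchmarks in Aim 1 will provide proof that we can improve screening metrics". That proof concerns improving metrics and meeting customers' needs, and it depends on the milestones and benchmarks together.
- **That the sponsor should have to place the lower confidence limit at 65% or above.** With 200 clients this needs 144/200 (72%), which has 30% power at a true 70% and 86% at 75%. That would impose a confirmatory test on a pilot.

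**Conclusion.** The concern holds in a limited form. The Aim 1 conclusion is worded more strongly than the planned analysis can support, because no uncertainty is attached to the 65% rate. A result exactly on target would be compatible with true rates from 58.0% to 71.6%.

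The interval rests on n = 200, and sections 6 and 9 do not agree on whether that is a ceiling or a floor. The pass probabilities rest in addition on a rule that the plan does not state. Whichever rule is meant, a yes-or-no verdict is unreliable for true rates near the target.

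The study is not invalidated, and the Aim 2 power figure is unaffected. This is a correction to reporting and wording that should be made before the Phase I report is written.

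**What to change.** 1. In section 8, change the Aim 1 statement so that the study will *estimate* the proportion of clients reached who complete screening.
2. Report exact (Clopper-Pearson) 95% confidence intervals for the overall, colonoscopy and stool-test rates. State the expected precision of the overall rate, about ±7 points at n = 200. For the stool-test rate, use the actual number of clients without colonoscopy as the denominator, not a fixed 140.
3. Describe the 65% target and milestones 1a and 1b as feasibility go-ahead benchmarks. Say whether the pooled 65% or both milestones apply, whether 1b means 70 tests or 50% of the remainder, and what the overall denominator is.
4. Do not add a 144/200 threshold as a new hurdle.

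The change needs no further clients or data. It costs three intervals and a few sentences, and the headline conclusion becomes slightly less favourable.

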Disparities and low screening rates exist primarily because of a host of structural (e.g., access, transportation) and individual barriers (e.g., fear, negative affective associations, daily life issues) experienced by lower income and minority patients that are generally beyond the scope of clinical practices and health insurance companies to address. Approaches to address these barriers have been proven effective by our team and others for various screening services but have not been tested as a marketable commodity. These proven methods include the use of patient navigation,^{8,9} culturally appropriate education,^{10,11} and community-based participatory processes.^{12,13} However, navigation services are not reimbursable expenses for clinical providers, require specialized expertise and access to multiple ancillary services (e.g., transportation). Health insurers have experimented with monetary incentives, reminders and incentivizing health providers, but these approaches are limited and do not address the basic structural and individual barriers influencing behaviors. But if proven to reduce “gaps in care”—insurance companies *will* outsource and pay for these services (e.g., see Letters; and National Witness Project (NWP) in Facilities and Resources). Effective programs offering multi-level services to optimize screening for non-adherent clients are not readily available for insurers or clinicians to adopt or purchase. Witness CARES, LLC proposes to remedy this gap by offering a full-service resource for educating, activating and navigating clients to screening for insurance companies (e.g., YourCare, see Letter) and for primary care clinics (e.g., Mercy Comprehensive Care Center, see Letter). Moreover, although there is an extensive body of work examining decision-making predictors of successful CRC screening,^{14,15} there are not easily implementable tools for predicting compliance in real time, or to assess for which clients at-home stool testing versus colonoscopy screening is likely to be most achievable. This STTR Phase I study provides an opportunity for Witness CARES, LLC to explore the feasibility of providing these services to Medicaid clientele to satisfy the screening expectations of insurers and primary care providers (Aim 1), and the feasibility of developing a predictive tool(s) (Aim 2) for determining which screening test is most appropriate for clientele.

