Proposed Data Collection (Milestone 2b). For this secondary data analysis, as a part of the Aim 1 methods described above, navigators will invite all clients contacted to complete assessment items via telephone. Based on prior research and navigation experience, we know that clients are willing to complete health assessments and surveys of up to ~130 questions by phone if incentivized. This telephone assessment includes 118 self-report questions all of which have been used by the current team members with African American and Medicaid clients. However, we have never combined all of these items, and expect this to increase our capacity to identify impactful predictors. Based on prior experience, we are adding a Patient Activation Measure (PAM),²⁹⁻³² Process of Change (POC)^{33,34} for CRC screening and a 3-item unpublished, Navigator Subjective Assessment/Predictor (NSAP) by the navigator at the completion of the other questions (based on recent experiences by [name] and [name]). A similar data analysis strategy will be applied here. The 118 items will be used to predict differentiation of screeners from non-screeners as well as, among screeners, those who chose FIT versus colonoscopy (COL). Together, these are expected to significantly increase our predictive capacity for colonoscopy outcomes. We anticipate (Milestone 2b) being able to complete the survey with at least 160 clients during this Phase I.

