7.1 Inclusion Criteria

Witness CARES, LLC will develop and obtain business agreements with YourCare and Mercy Comprehensive Care Center (MCCC) as required by these businesses to allow them to provide lists of their clients who are ages 50 and over and are non-adherent to CRC screening over the past year (i.e., no stool testing in past 11 months or colonoscopy for over 9 years). The clients will be Medicaid or Medicaid/Medicare subscribers. Uninsured patients may be included from MCCC, but will only be eligible for services to obtain FIT tests through the NYS Cancer Services Program.

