9 INFORMED CONSENT

Human Subjects Involvement and Characteristics. Witness CARES, LLC will develop and obtain business agreements with YourCare and Mercy Comprehensive Care Center (MCCC) as required by these businesses to allow them to provide lists of their clients who are ages 50 and over and are non-adherent to CRC screening over the past year (i.e., no stool testing in past 11

months or colonoscopy for over 9 years). The clients will be Medicaid or Medicaid/Medicare subscribers. Uninsured patients may be included from MCCC, but will only be eligible for services to obtain FIT tests through the NYS Cancer Services Program.

Once Witness CARES, LLC receives these lists they will do the following:

- 1) Begin calling clients and explaining that they are working collaboratively with their insurer or clinic to provide additional services for clients needing CRC screening. This initial call will allow WC Services to determine working/accurate telephone numbers and confirm that clients have not obtained CRC screening. We anticipate calling clients from the list (expected to be up to 2000 clients) until we successfully reach at least 200 clients. Witness CARES, LLC will send insurer and health clinic the lists with results of non-working numbers, patients no longer at numbers, etc.
- 2) Use an existing CRC navigation assessment to inquire about the client's knowledge and understanding of CRC screening. Depending on the results of this assessment, the navigator may a) determine some basic information about potential services the client will need to obtain screening (stool or colonoscopy), and establish a plan with the client to provide these services with a timeline; or b) send the client additional information by mail, email or text for a smart phone for the client to review, and establish a call-back appointment time.

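### The FIT-versus-colonoscopy comparison does not separate clients for whom colonoscopy was unavailable, so if any enrol, a service rule can appear as a client predictor

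*Combined protocol and SAP*

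**What the plan says.** Section 8 (Expected outcomes of Aim 1) sets Milestone 1b as stool screening for "70 of the 140 colonoscopy non-adherent clients (50% of clients refusing/ineligible for colonoscopy". The pool of 140 is thus described as holding both clients who decline colonoscopy and clients who cannot have it.

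The Aim 2 paragraph of the same section carries the Aim 1 targets forward: "In Aim 1 we expect 60 COL and 70 FIT subjects". Within the screened subset, "measures will be compared between those who chose FIT versus COL using the Mann-Whitney U test". A multivariable logistic model "may be considered to identify potential independent factors associated with screening choice". Section 5 (Proposed Data Collection, Milestone 2b) likewise uses the survey items to distinguish, "among screeners, those who chose FIT versus colonoscopy (COL".

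Section 7.1 defines one group limited to a single test: "Uninsured patients may be included from MCCC, but will only be eligible for services to obtain FIT tests". Section 9 repeats that they "will only be eligible for services to obtain FIT tests through the NYS Cancer Services Program". Insurance is among the demographic measures in Table 1.

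The only restriction on the FIT-versus-COL analysis is that the client was screened. No section excludes, flags or stratifies clients without access to colonoscopy. The comparison of the two client sources in Section 8 is a descriptive part of Aim 1 and does not address this.

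**The concern.** Section 2 gives the purpose of the tool: "to assess for which clients at-home stool testing versus colonoscopy screening is likely to be most achievable". For a client limited to FIT, the service rule answers that before any survey item is asked. Such a client adds nothing about which characteristics lead people with both options to one test or the other, yet would be counted in the FIT group.

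Two things could follow if such clients enrol and complete FIT. Insurance status would separate the groups because no uninsured client can reach COL through the service. Measures related to insurance, such as socioeconomic status or access to a primary care physician, could be pulled the same way, more weakly. Both could pass into the prototype that Section 8 says will be taken to Phase II. If insurance were entered in the optional logistic model, its coefficient would have no finite maximum-likelihood estimate, since one cell is empty by rule.

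**Working it through.** **Inputs.** From Section 8: 60 COL, 70 FIT, difference 0.5 SD, alpha 0.05 (taken as two-sided), stated power 80%. From Sections 8 and 5: survey expected from 160 of 200 contacted (80%). From Section 5: about 100 clients from MCCC. Not given: k, the number of FIT-only clients among the 70 FIT completers. It is varied below.

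**1. The plan's own power.** Power = Φ(0.5/SE − 1.96), with SE = √[(1/n1 + 1/n2)/e], where e = 1 for normal theory and e = 3/π = 0.955 for Mann-Whitney with normal data.
- Normal theory, 60/70: SE = 0.176, power 81.1%.
- Mann-Whitney, 60/70: SE = 0.180, power 79.3% (79.1% by simulation).

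The stated 80% is reproduced.

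**2. Insurance status under the rule alone.** Put k uninsured among 70 FIT and 0 among 60 COL. The Mann-Whitney statistic departs from its null mean of 2100 by 30k. Its tie-corrected variance is (60·70/12)·[131 − Σ(t³−t)/(130·129)], with tie groups of k and 130 − k. For k = 5 the departure is 150, the SD is 71.3, and z = (150 − 0.5)/71.3 = 2.10.

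| k | Mann-Whitney p | Fisher p |
|---|---|---|
| 4 | 0.062 | 0.124 |
| 5 | 0.036 | 0.061 |
| 6 | 0.021 | 0.030 |
| 10 | 0.0024 | 0.0018 |

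At the milestone's 50% uptake, 5 uninsured completers would need about 5/0.5 = 10 uninsured clients among the roughly 100 from MCCC.

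**3. Correlated measures.** Simulated Mann-Whitney rejection rate for a normal measure with no FIT–COL difference among clients who have both options, with the k FIT-only clients shifted by an assumed 0.5 or 1 SD:

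| k | 0.5 SD shift | 1 SD shift |
|---|---|---|
| 6 | about 5% | about 7% |
| 10 | about 6% | about 11% |
| 15 | about 9% | about 18% |

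With those k clients removed, the rate is about 5% throughout.

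**4. Power after restriction.** Mann-Whitney, 0.5 SD, using the formula in step 1:

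| FIT clients removed | COL/FIT | Power |
|---|---|---|
| 0 | 60/70 | 79.3% |
| 6 | 60/64 | 77.6% |
| 10 | 60/60 | 76.3% |
| 20 | 60/50 | 72.3% |

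**5. Survey completion.** The 60 and 70 are counted from 200 contacted, but the measures exist only for clients who are surveyed. If completion is unrelated to screening, the analysed numbers are 0.8 × 60 = 48 and 0.8 × 70 = 56. Power is then 70.0% before any restriction.

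**The case against.** The strongest reply is that the problem may never arise. Sections 7.1 and 9 only permit uninsured patients, only from MCCC, directly after saying that clients will be Medicaid or Medicaid/Medicare subscribers. A reader might infer from the Milestone 1b wording that some of the 70 FIT completers are known to be ineligible for colonoscopy. The documents do not say so: the phrase describes the 140, and how many of either group are ineligible is not stated. This stands, and it makes the point conditional.

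A second reply is that the expected outcome in Section 8 is phrased as completion, and uninsured status truly predicts completing FIT. That is fair as far as it goes, and it means the insurance association would be real, not spurious. But under either reading the test is fixed by the rule, so the association restates the rule and says nothing about clients with a choice.

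Third, the effects are small or obvious. Anyone who knows the rule would recognise an insurance effect, and correlates are little affected below about 10 clients. With 118 items each tested at 0.05 and no true differences, about 118 × 0.05 = 6 would reach significance by chance anyway, in an exploratory pilot to be retested. This stands as a limit on importance.

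Fourth, insurance status is already collected and navigators already assess each client's capacity to obtain colonoscopy. That makes the fix easier, but the analysis text makes no use of either. The logistic model is optional, so the estimation failure is contingent too.

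**Conclusion.** The point holds in conditional form. The analysis set does not distinguish clients who could have had either test from those who could have only one, although the plan itself provides for the latter. With about 5 or more uninsured FIT completers, insurance status can reach nominal significance from the service rule alone. Its correlates show only mild inflation, about 6–11% with 10 such clients under the assumed 0.5–1 SD shift, and very little below that. The count is not in the documents and may be zero, so no size of bias can be asserted for this trial.

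A reader might also infer that the stated 80% power is miscalculated. It is not: it reproduces for 60 versus 70. It does rest on every screened client being surveyed, which differs from the plan's own 80% expectation. This is a cheap improvement to the analysis set, not a defect that invalidates the pilot.

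**What to change.** - At the first needs call, record whether colonoscopy is available to the client and, if not, why (uninsured, medical, other). This is one field in the monitoring system that Section 8 already plans.
- Run the FIT-versus-COL Mann-Whitney tests, and any logistic model, in screened clients for whom both tests were available, grouped by test completed. Use that term in place of choice in Sections 5 and 8.
- Keep FIT-only clients in Milestone 1b and report their number and characteristics separately. An all-screened analysis can stay as a sensitivity analysis.
- Restate the power for the numbers expected to be analysed, allowing for survey completion.

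The cost is one data field, a few sentences, and the power loss shown in step 4: 2 to 3 points for 6 to 10 clients removed, 7 points for 20. If no FIT-only client enrols, the restriction changes nothing. The restricted result will not describe FIT-only clients, whose test the rule already determines.
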